6.4.3 Liver Function Laboratory Parameters

The number of participants with laboratory abnormalities will be provided for SAF for the following liver function laboratory parameters. The table will be provided for both baseline and post-baseline measurements. The measurements from both scheduled / unscheduled visits will be used. The ratio to the upper limits of normal (ULN) will be used for these parameters.

- Alanine aminotransferase (ALT): $> 2xULN - \leq 3xULN$, $> 3xULN - \leq 5xULN$, $> 5xULN - \leq 8xULN$, $> 8xULN$
- Aspartate aminotransferase (AST): $> 2xULN - \leq 3xULN$, $> 3xULN - \leq 5xULN$, $> 5xULN - \leq 8xULN$, $> 8xULN$
- Total bilirubin (TBL): $> 2xULN$
- alkaline phosphatase (AP): $\geq 1.5xULN$
- γ -GT (gamma GT): $\geq 2xULN$
- International normalized ratio (INR): $> 1.5xULN$

In addition, frequency tables based on categories above and box plot for measurements over time by visit will be provided.

The number of participants with postbaseline elevated liver values according to the following criteria will be provided:

- $> 3xULN$ of ALT or AST accompanied (using the values taken from the same serum sample) by $> 2xULN$ of TBL, or
- $> 3xULN$ of ALT or AST accompanied by $> 1.5xULN$ of INR, or
- participants who reported unspecific symptom (fatigue, nausea, vomiting, right upper abdominal quadrant pain or tenderness, fever, rash and/or eosinophilia) with the CRF pages: Clinical Signs and Symptoms with elevated liver enzymes / Clinical Signs and Symptoms with elevated liver enzymes (Follow-up)
 - For participants with eosinophilia, only the case if their measurement of laboratory parameter of Eosinophils/Leukocytes $> 5\%$ will be included into the analysis.

A subject listing will be provided for those participants.

The eDISH plot (maximum of ALT postbaseline value \times maximum of TBL postbaseline value) will be provided. A line plot of AP, ALT, AST and TBL over time will be provided for participants with liver injury (ALT $>5xULN$).

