Original Protocol	1.0	25 SEP 2020								

Protocol Amendment Summary of Changes Table

Amendment 2 (27 JAN 2022)

This amendment is considered to be substantial based on the criteria set forth in Article 10(a) of Directive 2001/20/EC of the European Parliament and the Council of the European Union.

Overall Rationale for the Amendment:

Bayer has decided for a clinical hold with an immediate stop of treatment of this Phase 2b study with BAY 1817080.

Considering one confirmed and one potential case of drug-induced liver injury (DILI) in patients exposed to BAY 1817080 for 812 weeks of treatment during the phase 2 program in all indications, the benefit-risk ratio for the ongoing study 20584 is no longer considered to be positive.

No new patients should be enrolled into the study and no study participants should be randomized.

Study participants who are currently treated should immediately stop treatment and participants who have been randomized should not start treatment with the study drug, respectively. Study participants randomized to the open label elagolix arm can continue taking tablets from the current blister but must not start with a new one.

All participants should come to the end of treatment and follow up visits as soon as possible.

Following are the description of change and a brief rationale.

Section # and Name	Description of Change	Brief Rationale
Section 1.3 Schedule of Activities (SoA) Section 1.2 Schema Section 4.1 Overall Design	Visits 5a and 6a were added for additional safety laboratory tests. All participants, except those randomized to elagolix, will have a 90-day follow up	Comprehensive safety follow up of study participants exposed to BAY1817080
Section 2.3.1 Risk Assessment	Text on potential changes in liver function laboratory parameters updated	Updated benefit/risk assessment
Section 2.3.3 Overall Benefit-Risk Conclusion	Text updated to reflect the updated benefit/risk assessment	Updated benefit/risk assessment
Section 8.3.7 Adverse Events of Special Interest Section 10.6.2 Close observation of participants with ALT or AST > 3 x ULN	Abnormal laboratory results meeting the criteria of transaminases (ALT and/or AST) >8x ULN or >3x ULN with total bilirubin >2x ULN will be reported as adverse	Comprehensive safety follow up of exposed study participants

Clinical Study Protocol Global Amendment 2 BAY 1817080/ 20584

27 JAN 2022 Page: 3 of 99

	events of special interest.	

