8.3.1 Time Period and Frequency for Collecting AE and SAE Information

All AEs and SAEs will be collected from the signing of the ICF until the follow-up visit, i.e., Visit 6 or 7, respectively, at the time points specified in the SoA (Section 1.3).

Additional details on smell and taste related AEs will be collected once at the end of an individual's study participation via dedicated eCRF pages.

All SAEs will be recorded and reported to the sponsor or designee immediately and under no circumstance should this exceed 24 hours of learning of the event, as indicated in Section 10.3. The investigator will submit any updated SAE data to the sponsor within 24 hours of it being available.

27 JAN 2022 Page: 59 of 99

Investigators are not obligated to actively seek information on AEs or SAEs after conclusion of the study participation. However, if the investigator learns of any SAE, including a death, at any time after a participant has been discharged from the study, and he/she considers the event to be reasonably related to the study intervention or study participation, the investigator must promptly notify the sponsor.

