4.1 General Principles

The statistical evaluation will be performed by using the software SAS (release 9.4 or higher; SAS Institute Inc., Cary, NC, USA) and ValidR (version 3.5.2 or higher; Mango Solutions Ltd., UK)[1].

All variables will be analyzed by descriptive statistical methods. The number of data available and missing data, arithmetic mean, standard deviation, minimum, quartiles, median, and maximum will be calculated for metric data. Frequency tables will be generated for categorical variables. Where appropriate, the individual change from baseline will also be analyzed.

Unscheduled/extra assessments (e.g. laboratory data or vital signs) associated with non-protocol visits will be included in listings, but not in any visit-based summary tables.

In general, confidence intervals (CIs) will be two-sided with a confidence level of 95 %. For the primary analysis of the primary efficacy variable only, 80% CIs will be reported in addition for consistency with the one-sided α -level of 10%.

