6.4.1 Adverse events (AEs)

All AEs will be collected from signing the informed consent until the SFU visit.

A treatment-emergent AE (TEAE) is defined as any event arising or worsening after the start of study drug administration until 14 days after the last study medication intake.

The incidence of TEAEs will be assessed as secondary safety endpoint. The incidence of AEs and TEAEs will be analyzed by descriptive statistics, such as frequency tables.

An overall summary of the number and percentage of participants with AEs and TEAE will be presented. In addition, all AEs and TEAEs will be tabulated according to the affected system organ class and preferred term, as coded by the Medical Dictionary for Regulatory Affairs (MedDRA).

The frequency of the AEs related to potential and identified risks of Eliapixant will be displayed. Regarding the identification specifications for these AEs, the following SMQs and PTs will be applied:

1. SMQ “Taste and smell disorders”

2. SMQ “Hemorrhages”
3. MLG Hypotension
 - PT: Blood pressure ambulatory decreased;
 - PT: Blood pressure decreased;
 - PT: Blood pressure diastolic decreased
 - PT: Blood pressure systolic decreased;
 - PT: Diastolic hypotension
 - PT: Hypotension;
 - PT: Mean arterial pressure decreased
 - PT: Heart rate decreased
 - PT: Bradyarrhythmia
 - PT: Bradycardia
 - PT: Sinus bradycardia
 - PT: Dizziness
 - PT: Dizziness postural
 - PT: Dizziness exertional
 - PT: Syncope
 - PT: Presyncope
 - PT: Loss of consciousness
 - PT: Blood pressure orthostatic decreased;
 - PT: Orthostatic hypotension;
4. SMQ “Drug related hepatic disorders - comprehensive search”

Further tables will be provided for serious and/or drug related TEAEs. Tables for non-serious TEAEs will also be provided.

In addition, a separate table summarizing TEAEs that occurred in more than 5% of the subjects will be provided.

The incidence of all AEs during pre-treatment and during post-treatment (that is, AEs occurring more than 14 days after end of treatment with study drug) will be tabulated separately.

The summaries will be tabulated by intervention group and overall.

Serious adverse events, deaths and adverse events leading to discontinuation will be listed. The date, relative day (to study intervention) and treatment-emergent flag will be included.

Further summaries of adverse events by intensity and worst outcome, may be provided, consistent with Bayer Global Medical Standards.

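### Cumulative safety displays that include elagolix make no allowance for its sparser liver sampling and shorter follow-up under the current protocol

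*SAP*

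**What the plan says.** **Schedule.** Protocol 2.3.1 sets liver tests every 2 weeks for BAY 1817080 and every 4 weeks for elagolix. The Schedule of Activities (Protocol 1.3) excludes elagolix participants from the extra liver visits 2a, 3a, 4a, 5a and 6a. Protocol 10.2 limits those extra draws to AP, ALT, AST, GGT and total bilirubin. Protocol 4.1 gives at least 90 days of follow-up in the blinded arms and at least 38 days on elagolix. Under Protocol 8.3.1, adverse events are collected "until the follow-up visit, i.e., Visit 6 or 7, respectively".

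**When the schedule changed.** Visits 2a to 4a came with Amendment 1 (22 JUN 2021; Protocol 10.11.1). Amendment 2 (27 JAN 2022) records that "Visits 5a and 6a were added for additional safety laboratory tests" and moves all arms except elagolix to 90 days. It also stopped dosing: "Study participants who are currently treated should immediately stop treatment", whereas "Study participants randomized to the open label elagolix arm can continue taking tablets from the current blister".

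**Displays.** SAP 6.4.3 counts participants with liver abnormalities before and after baseline ("The measurements from both scheduled / unscheduled visits will be used") and plots maximum ALT against maximum bilirubin (eDISH). It does not say that the counts are by arm; that is inferred. SAP 6.4.4.1 gives shift tables by timepoint and for the worst post-baseline value. SAP 6.4.1 tabulates events more than 14 days after treatment separately, and "The summaries will be tabulated by intervention group and overall". All of this uses the safety set, which includes elagolix.

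**Follow-up 2.** Protocol 1.2 and 4.1 apply it to everyone except elagolix. Protocol 4.2 says about half of randomized participants. The SAP Figure 1 footnote says the first half only. The text of SAP section 3 says all participants, but ends in an unexplained 'respectively'.

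**The concern.** A count of participants who ever had an abnormal value rises with the number of samples, and a count of participants with any event rises with the time observed. Two arms with identical true risk will therefore show different counts if one is sampled more often or watched for longer. Here the arm sampled less and followed for less time is elagolix, so it looks safer.

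This matters because safety against elagolix is part of a secondary objective (Protocol section 3), elagolix carries its own transaminase warning (Protocol 2.3.1), and dosing was stopped because of liver injury. The SAP is based on Amendment 2, and its liver analyses were revised after both schedule changes. It nevertheless plans no shared window, person-time rate or caveat for these displays, and no summary of liver tests or follow-up days per arm. A reader could not correct for the imbalance from the planned tables.

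**Working it through.** **1. The plan's own schedule.** Over 84 days, 84/14 = 6 panels (days 14, 28, 42, 56, 70, 84) and 84/28 = 3 panels (days 28, 56, 84). This reproduces the visit columns. In follow-up under Amendment 2, the blinded arms are sampled at 14, 38, 68 and 90 days after last dose (4) and elagolix at 38 days (1). The total is 10 v 4. INR is not in the extra panel: 3 v 3 on treatment and 2 v 1 in follow-up, so 5 v 4.

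**2. Detecting one elevation of D days.** The documents give no duration, so D is an assumption shown as a range. With a uniform onset and the same onset rate in all arms, the expected number detected is proportional to the sum, over gaps between panels, of min(D, gap). The table gives blinded / elagolix.

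| Schedule (panels) | D = 7 | D = 14 | D = 21 | D = 28 |
|---|---|---|---|---|
| Before Amendment 1, on treatment (3 v 3) | 1.0 | 1.0 | 1.0 | 1.0 |
| Amendment 1 onward, on treatment (6 v 3) | 42/21 = 2.0 | 84/42 = 2.0 | 84/63 = 1.33 | 84/84 = 1.0 |
| Amendment 1 through Visit 6 (7 v 4) | 49/28 = 1.75 | 98/56 = 1.75 | 105/84 = 1.25 | 112/112 = 1.0 |
| Full Amendment 2 schedule (10 v 4) | 70/28 = 2.5 | 140/56 = 2.5 | 161/84 = 1.92 | 172/112 = 1.54 |

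The gaps are 6×14 v 3×28 on treatment, with 38 added to both arms through Visit 6. The last row uses 7×14, 24, 30 and 22 v 3×28 and 38. It is a ceiling, because it also counts new onsets during the longer follow-up at a constant background rate.

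**3. Who can have which schedule** (assuming each amendment took effect on its date, and that elagolix has no Visit 7).
- Treated wholly before 22 JUN 2021: 3 v 3 on treatment.
- Under Amendment 1 without Follow-up 2: the study ends at Visit 6, at most 41 days after last dose. Anyone with last dose by 16 DEC 2021 had finished by 26 JAN 2022 and stays at 7 v 4.
- Higher counts need assignment to Follow-up 2, or follow-up not yet finished when Amendment 2 took effect.
- The full 10 v 4 needs a completed day 84 and Visit 5a still possible on 27 JAN 2022. Visit 5a is at the latest 17 days after last dose, so last dose falls between 10 and 27 JAN 2022 (18 days).
- Stopped by the hold at day 28: 1 + 1 + 4 = 6 v 0 + 1 + 1 = 2 (earlier panels, Visit 5, follow-up). At day 56: 3 + 1 + 4 = 8 v 1 + 1 + 1 = 3. Both ignore any elagolix blister finished after the hold.

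**4. Post-treatment adverse events under Amendment 2.** 90 − 14 = 76 days v 38 − 14 = 24 days; 76/24 = 3.2. With ±3-day visit windows the ratio runs from 73/27 = 2.7 to 79/21 = 3.8. At an equal constant rate, risk p in 24 days becomes 1 − (1 − p)^(76/24): 2% becomes 6.2%, 5% becomes 15.0% and 10% becomes 28.4%. These rates are illustrative. For participants followed under a 50% rule applied equally to all arms, the ratio is 1.0.

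**The case against.** The strongest reply is that the plan already contains most of what a careful reader needs. SAP 6.4.3 adds that "frequency tables based on categories above and box plot for measurements over time by visit will be provided" (less help if 'by visit' belongs only to the box plot). Unscheduled values "will be included in listings, but not in any visit-based summary tables" (SAP 4.1). Shift tables are by timepoint. There are subject listings for the combined liver criteria, line plots over time for participants with ALT above 5 times ULN, and listings with relative day for serious events, deaths and events leading to discontinuation. Protocol 2.3.1 reports one close-liver-observation case in this study as of 16 DEC 2021; with so few cases, individual review tells more than a detection ratio. The endpoint paired with the safety objective, treatment-emergent events, has the same 14-day window in every arm. Elagolix is described as exploratory (Protocol 9.2), is open label and was not used in Japan or China, so no table makes it fully comparable.

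All of that stands, and it limits the size of the point. It does not cover the cumulative displays themselves.

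Three stronger readings are tempting but not supported:
- *That 6 v 3 or 10 v 4 describes the whole trial.* Both depend on the amendment in force, and enrolment dates are not given.
- *That the post-treatment event table is open-ended.* SAP 6.4.1 ends collection at the safety follow-up visit. The end point exists but differs between arms.
- *That the liver tables should be rebuilt on shared visits.* This would discard values from visits added to detect liver injury and could understate BAY 1817080 signals.

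**Conclusion.** The point holds as a minor, descriptive one. For participants under Amendment 2, the post-treatment adverse-event table compares 76 with 24 days of observation. The cumulative liver displays compare 6 with 3 panels on treatment for anyone treated wholly under Amendment 1 who completed day 84. The liver tilt on treatment is 2.0 for elevations of 14 days or less, 1.33 at 21 days and nil at 28 days or more. The realised trial-wide imbalance cannot be computed from the documents.

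The direction is against the blinded arms, placebo included. BAY 1817080 versus placebo is unaffected because those arms share one schedule, and no hypothesis test is touched. The treatment-emergent window is common to all arms, although hepatic events found only through a laboratory value still depend on how often blood is drawn. It would be wrong to infer that the BAY 1817080 liver findings are an artefact of sampling. The conclusion rests on equal true rates, uniform onset, the assumed durations, amendments effective on their dates, and the inference that the SAP 6.4.3 counts are shown by arm.

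**What to change.** - **SAP 6.4.1:** add a table of post-treatment adverse events truncated at 38 (+3) days after last dose, or expressed per person-time, by arm.
- **SAP 6.4.3 and 6.4.4.1:** keep the full cumulative tables and the eDISH plot as the main display. Report the number of liver tests and follow-up days per participant by arm, footnote the unequal schedule, and state whether the liver counts are by treatment group.
- **Optional only:** a cumulative liver count limited to Visits 3, 4, 5 and 6, labelled as possibly understating BAY 1817080 signals and never replacing the full tables. It would not equalise exposure either, given the different handling of elagolix at the hold.
- **Follow-up 2:** reconcile Protocol 1.2 and 4.1, Protocol 4.2, SAP Figure 1 and the text of SAP section 3.

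The cost is a footnote and a small amount of extra tabulation from data already collected. If only one step is taken, the footnote with tests and follow-up days per arm is the cheapest.

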8.3.7 Adverse Events of Special Interest

Adverse events of special interest have to be reported to the sponsor along the timelines set for SAEs, i.e. within 24 hours of the investigator's awareness, as described in Section 8.3.1.

Declaration of an event as serious should only occur if one or more of the serious criteria is applicable. Non-serious adverse events of special interest should not automatically be upgraded to serious by the reporting investigator.

Adverse events of special interest are liver enzyme increases meeting the following criteria:

- ALT and/or AST >8x ULN OR
- ALT and/or AST >3x ULN with total bilirubin >2x ULN.

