10.6.1 Liver safety -related monitoring and discontinuation criteria

Investigators and participants should pay special attention to non-specific symptoms which may be associated with liver dysfunction; including anorexia, nausea, fatigue, right upper abdominal discomfort, vomiting, malaise, jaundice, fever, and rash.

- Information on these symptoms should be asked for in case of abnormal liver laboratory values (see Table 10–2) or any other suspicion of liver dysfunction.
- Participants should be regularly reminded to contact the investigator immediately if they are concerned about such symptoms, and unscheduled visits for evaluation should be considered

Table 10-2: Liver Safety-Related Monitoring and Discontinuation Criteria

Lab manulé	Manageman
Lab result	Measures
ALT or AST > 3 x ULN	 Initiate close observation as defined in Section 10.6.2. Consider withdrawal of study intervention if the participant does not adhere to procedures required for close observation^a
ALT or AST > 3 x ULN and TBL > 2 x ULN	Withdraw study intervention
ALT or AST > 3 x ULN and INR > 1.5 x ULN	Withdraw study intervention
ALT or AST > 3 ULN with appearance of fatigue, nausea, vomiting, right upper abdominal quadrant pain or tenderness, fever, rash and/or eosinophilia (>5%)	Withdraw study intervention
ALT or AST > 5 x ULN for more than 2 weeks	Withdraw study intervention
ALT or AST > 8 x ULN	Withdraw study intervention

Abbreviations: ALT = alanine aminotransferase; AST = aspartate aminotransferase; INR= international normalized ratio, TBL = total bilirubin, ULN = upper limit of normal (all referring to serum/plasma)

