10.6.2 Close observation of participants with ALT or AST $> 3 \times \text{ULN}$

- Abnormal laboratory results and clinical signs and symptoms resulting in close liver observation should be reported as adverse event.
- Abnormal laboratory results meeting the criteria of transaminases (ALT and/or AST) >8x ULN or >3x ULN with total bilirubin >2x ULN will be reported as AEs of special interest (see Section 8.3.7).
- It is critical to initiate close observation immediately upon detection and confirmation of early signals of possible drug-induced liver injury, and not to wait until the next scheduled visit or monitoring interval
- Procedures to be taken resemble workup/ documentation along the guideline of the US FDA for assessment of potential drug-induced liver injury (38). Objectives are to:

a in case visits for close observation could not be arranged with a frequency deemed adequate by the investigator, despite of reasonable efforts

27 JAN 2022 Page: 87 of 99

- Ensure participant safety
- o Identify possible non-study-intervention-related causes of liver injury
- A close observation has to be initiated during intervention or follow-up phase if ALT or AST reaches >3 x ULN. Close observation includes:
 - o Sampling for the first batch of laboratory parameters (see Table 10–3).
 - Repeating follow-up samplings (see Table 10–3).2 to 3 times per week.
 Frequency of retesting can decrease to once a week or less if abnormalities stabilize.
 - Obtaining a detailed history of the symptoms and prior or concurrent diseases
 - Obtaining a history of concomitant drug use (including nonprescription medications and herbal and dietary supplement preparations), alcohol use, recreational drug use, and special diets.
 - Ruling out acute viral hepatitis, autoimmune or alcoholic hepatitis, nonalcoholic steatohepatitis, hypoxic/ischemic hepatology and biliary tract disease. This may require performing additional procedures, e.g. ultrasound examinations. If requested, tests will be done retrospectively using residual blood/serum samples collected at visits before laboratory abnormalities occurred.
 - o Obtaining a history of exposure to environmental chemical agents
 - Obtaining additional tests to evaluate liver function as required (e.g. INR, direct bilirubin measurements)
 - Liver imaging
 - o Considering gastroenterology or hepatology consultations
- Data for any findings are to be recorded in the corresponding eCRF pages
- Stopping criteria for close observation:

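### The composite liver-case count and listing in SAP 6.4.3 omit two of the protocol's five liver withdrawal patterns and one of its two special-interest patterns, and the liver plots are triggered by ALT alone

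*SAP*

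**What the plan says.** Protocol 10.6.1, Table 10-2, gives five laboratory patterns that lead to withdrawal of study intervention, all expressed in ALT or AST. They are "ALT or AST > 3 x ULN and TBL > 2 x ULN"; "ALT or AST > 3 x ULN and INR > 1.5 x ULN"; above 3xULN with listed symptoms or eosinophilia; "ALT or AST > 5 x ULN for more than 2 weeks"; and above 8xULN with no further condition.

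Protocol 8.3.7 makes two patterns adverse events of special interest: ALT and/or AST above 8xULN alone, and "ALT and/or AST >3x ULN with total bilirubin >2x ULN". Protocol 10.6.2 repeats this pair ("Abnormal laboratory results meeting the criteria of transaminases (ALT and/or AST) >8x ULN or >3x ULN with total bilirubin >2x ULN").

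SAP 6.4.3 specifies these liver outputs:

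- Category tables, separately for ALT and AST, with a top category above 8xULN, using scheduled and unscheduled samples.
- A composite count of participants meeting any of three criteria, with a subject listing for those participants only. The bilirubin criterion is a value above 3xULN "of ALT or AST accompanied (using the values taken from the same serum sample) by" bilirubin above 2xULN. The INR criterion has no timing condition. The symptom criterion refers to the CRF pages for elevated liver enzymes and restates no ALT or AST threshold.
- "The eDISH plot (maximum of ALT postbaseline value" against the maximum bilirubin value).
- Line plots of AP, ALT, AST and bilirubin over time for participants with ALT above 5xULN.

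**The concern.** Amendment 2 stopped treatment because of one confirmed and one potential case of drug-induced liver injury across the phase 2 programme. It also introduced the special-interest definition. SAP section 1 states that the plan rests on that amendment, and SAP section 7 says that version 2.0 added analyses of close liver observation. A reader would therefore expect the dedicated liver count and listing to follow the protocol's own liver definitions. They do so only in part.

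What is at stake is whether the study report can be reconciled with the protocol. A participant can meet a withdrawal rule and a special-interest rule and still be outside the one output that looks like the liver-case list. No test, estimate, alpha or sample size is involved.

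**Working it through.** The plan gives no figure to reproduce, so the check sets the rules side by side and then runs hypothetical profiles through both sets.

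**Rules (all ALT or AST, multiples of ULN)**

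| Protocol pattern | Source | In SAP composite count and listing? | Other SAP 6.4.3 output |
|---|---|---|---|
| >3x with bilirubin >2x | Table 10-2 and 8.3.7 | Yes, same sample | eDISH, unmatched maxima, ALT only |
| >3x with INR >1.5x | Table 10-2 | Yes | ALT, AST and INR category rows |
| >3x with symptoms or eosinophilia | Table 10-2 | Yes, through CRF pages | – |
| >5x for more than 2 weeks | Table 10-2 | No | No duration derived; line plot if ALT >5x |
| >8x alone | Table 10-2 and 8.3.7 | No | Separate ALT and AST rows; line plot if ALT >5x |

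Withdrawal patterns covered: 5 − 2 = 3. Special-interest patterns covered: 2 − 1 = 1. No SAP output counts or lists participants by the 8.3.7 definition as such.

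The separate rows do not yield the number with ALT *or* AST above 8x. That number is the ALT count plus the AST count minus those with both, and the overlap is not tabulated.

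**Hypothetical profiles (no other finding unless stated)**

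| Profile | Protocol pattern met | SAP composite | Line plot |
|---|---|---|---|
| ALT 4x, bilirubin 2.5x, one sample | Bilirubin rule, special interest | Yes | No |
| ALT 4x, INR 1.6x | INR rule | Yes | No |
| ALT 4x with nausea on the CRF page | Symptom rule | Yes | No |
| ALT 9x, AST 6x | >8x, special interest | No | Yes |
| AST 9x, ALT 4x | >8x, special interest | No | No |
| ALT 6x on days 28 and 45 (45 − 28 = 17 days) | >5x for more than 2 weeks, if sustained between samples | No | Yes |
| Day 28: ALT 4x, bilirubin 1.5x; day 32: ALT 2.8x, bilirubin 2.5x | Bilirubin rule, only if one sample is not required | No | No |

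The fifth profile enters the eDISH plot at its ALT of 4x, so the AST of 9x is invisible there. The last is plotted at (4, 2.5), the pair of maxima, but is not in the composite count.

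The sustained pattern needs an explicit derivation. Nominal liver-sampling visits on treatment are 14 days apart (for example 28 − 14 = 14), and 14 days is not more than two weeks. Two successive scheduled samples at nominal timing would not establish the pattern, so unscheduled samples and a stated rule for consecutive values are needed.

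**The case against.** The strongest reply is that these participants do not disappear. ALT and AST above 8xULN are each counted by category. Protocol 10.6.2 asks that findings leading to close observation be reported as AEs. SAP 6.4.1 tabulates all AEs, displays a broad hepatic query and lists AEs leading to discontinuation. SAP 6.4.4.1 lists out-of-range values and includes unscheduled samples in the worst-value shift tables. SAP 6.3 highlights close-observation participants in the concentration plots. Table 10-2 is also a management table, not an analysis definition, and protocol 9.4.5 leaves safety details to the SAP.

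Most of that stands. It rules out the inference that liver cases go unreported or that the study report must show fewer cases than the sites did. It does not supply the missing derivation of sustained elevation, a special-interest count, or AST in the plots. The listing of AEs leading to discontinuation also cannot pick up an elevation first seen after the last dose. The management-table argument does not reach 8.3.7, which is a reporting definition.

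A reader might also infer that the same-sample condition contradicts the protocol. The documents do not show this: Table 10-2 and 8.3.7 join the two values without stating any timing, so the SAP makes explicit something the protocol leaves open. An unmatched plot and a matched count can be complementary, and the SAP states no eDISH quadrant limits.

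Nor are the SAP criteria uniformly narrower. The symptom criterion restates no ALT or AST threshold and could be wider than its Table 10-2 counterpart. Replacing it could lower the count.

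**Conclusion.** The point holds as a gap in descriptive safety reporting. Two of five withdrawal patterns and one of two special-interest patterns are outside the composite count and dedicated listing. Sustained elevation above 5xULN is derived nowhere, and AST-driven cases get no line plot and no AST contribution to the eDISH plot. The firmest parts are the two omitted patterns and the ALT-only plots. The sample-timing part is a matter of reconciliation, since the protocol is silent.

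The number of participants affected cannot be computed from the documents. By 16 DEC 2021 this study had contributed one of four reported transaminase cases in the programme, and nothing shows that this case falls outside the SAP criteria. With counts that small, a complete case list is worth having, but it would be wrong to claim that a case has been lost. The conclusion takes the SAP criteria as written and no view on which thresholds are right.

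**What to change.** In SAP 6.4.3, keep the three existing criteria and make these additions:

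- Add to the count and listing (i) ALT or AST above 8xULN and (ii) ALT or AST above 5xULN for more than two weeks, derived from scheduled and unscheduled samples with the rule for consecutive values stated.
- Add a by-arm row for participants meeting the protocol 8.3.7 special-interest definition.
- Keep the same-sample bilirubin count and add a row for ALT or AST above 3xULN and bilirubin above 2xULN at any post-baseline time, so that the count can be reconciled with the eDISH plot. No time window should be set, because the documents give no basis for one.
- Use the larger of ALT and AST, in multiples of ULN, in the eDISH plot, or add an AST version. Draw the line plot for everyone meeting any listed criterion.

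The cost is SAP wording, a few extra rows and some derivations on data already collected. The any-time row may include bilirubin rises unrelated to the transaminase rise, which is a reason to show it beside the same-sample row and not in place of it.
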